The summary should give a brief description of the central question that the research is intended to answer and its justification. It should specify the hypothesis (if applicable) and the research objectives. In addition, the synopsis should briefly describe the design, population, methods and procedures of the study. Finally, if applicable, the nature and extent of the burden and risks should be indicated.

Rationale

For intensive care staff in training, learning the steps in monitoring the function of an extracorporeal membrane oxygenator (ECMO) machine are fundamental concepts that form the basis on which their future practice will be built. The modality of this training is often practical in the form of an apprenticeship, shadowing experienced intensivists or perfusionists in order to learn their craft. We propose that if this initial training required more active participation in the form of a simulation, that trainees would learn these procedures more quickly and more reliably.

Over the past few years, emerging virtual reality (VR) applications have quickly gained broad attention within the medical field, including in cardiology and cardiothoracic surgery, as well as medical education more generally. Combining VR technology with head mounted displays (HMD), enables the design of a realistic, custom-built simulation in a 3 dimensional fully immersive environment [1]. Our group has developed a Virtual Reality (VR) simulation of the process of monitoring and performing a full circuit check for an ECMO patient. This Virtual Reality Extracorporeal Membrane Oxygenator Simulator (VR-ECMO sim) promises to update how we approach education of perfusionists and intensive care staff for their critical role.

In a related study on the VR-Extracorporeal Simulator (entitled “Virtual Reality Simulation as a Training Tool for Perfusionists in Extra Corporeal Circulation; Establishing Face and Content Validity” currently under peer-review), we showed that experts and novices alike found the simulator to be useful & realistic, and therefore valid for face and content validity. Due to the demonstration of feasibility in a closely related simulator, we aim to demonstrate face and content validity alongside concurrent validity in a single study for the VR-ECMO sim. We hypothesise that VR will enable participants to better learn and retain information through interactive engagement with a virtual reality simulator.

Objective(s)

Primary outcomes

The accuracy with which the predefined sequence of steps is performed by the participant, defined as number of mistakes made and time taken, and amount of prompts/assistance required from the expert perfusionist.

Secondary outcomes

[figure not shown]
Additional data include participants views on the advantages and disadvantages of virtual reality training in the context of ECMO.

Additional study parameters

Data will be collected on the participants age, gender, experience with ECMO, and experience with VR usage.

Study type

This will be a hybrid study, with an expert & novice face & content study, and contained within the novice group, a single blinded randomised controlled trial.

Study population

Our study will recruit from two populations for the expert and novice arms of this study. For the former, 10 experts who are experienced perfusionists/intensivists with more than 6 years of experience with ECMO will be included. For the novice arm, the population will include intensive care nurses & cardiothoracic surgery nurses who work at one of the academic hospitals in the Netherlands, with no prior experience with ECMO.

Methods

The study is broadly divided into two arms: expert (experienced perfusionists / intensive care staff) and novices (Intensive care staff who have no experience with ECMO) and is summarised in Figure 1.

Novice Arm (Randomised Controlled Trial)

Novice participants will be allocated a study ID from 1-50 at the point of recruitment and randomised by an online research randomiser (<https://www.randomizer.org/>) between the instructional video (control) group and VR-ECMO sim (intervention) group. The control group will watch a video in which a perfusionist explains how to perform a circuit check for an ECMO patient on VA ECMO. The participants are then individually assessed using a real ECMO machine and ECMO doll, whereby they are asked to repeat the steps that they have been trained in. This assessment is recorded on video to be assessed later by an expert assessor, and an expert perfusionist & assessor will be present during the assessment

to provide prompts when a student is unsure how to perform a certain step. After completion of the assessment, the VR group will be asked to fill out an objective questionnaire (Appendix 2) based on the standardised USE questionnaire [2] to assess baseline characteristics such as prior experience/training and the usefulness, satisfaction, and ease of use of the VR training modality. Participants from the control group will be given the option to also perform the VR training, and subsequently fill a USE questionnaire about their experience with VR.

Expert Arm

Expert participants will not be randomised, and will all perform the VR-ECMO sim before completing the USE questionnaire. Their data will be used for the face and content validity portion of this study.

Randomisation

Participants in the novice arm will be randomly assigned to either interventional or control group, using <https://www.randomizer.org/> as stated above to generate a group allocation for the participant according to their study ID number.

Blinding

Participants will not be blinded as the differences in the differing nature of the intervention versus control group do not allow for this. Selected study personnel, including those physically facilitating both groups during the intervention phase will not be blinded, as again the study design does not allow for this. Study personnel who facilitate the physical assessment for the novice arm, perform data collection & analysis, including the expert assessor for the video recording, will be blinded.

Burden and risks

We do not foresee any risks or burdens incurred with participation, aside from mild nausea which may occasionally occur during a virtual reality experience. This typically subsides quickly once the head mounted display is removed.

Recruitment and consent

Our study will recruit from two populations for the expert and novice arms of this study. For the former, 10 experts who are experienced perfusionists/intensivists with more than 6 years of experience with ECMO will be included. For the novice arm, the population will include intensive care nurses & cardiothoracic surgery nurses who work at one of the academic hospitals in the Netherlands, with no prior experience with ECMO. We calculated a required sample size of 44 novice participants (22 per group) in order to likely achieve statistically significant results.

The recruitment process will be performed by a combination of poster advertisements featuring a QR code where participants can sign up. These posters will be hung in areas where eligible staff are likely to gather e.g. break rooms. On the sign-up page, the participants will be asked to enter name and contact details, and then will be presented with the participant information form as attached as an appendix to this application. Once they have read this sheet, and agreed to it in the form by selecting 'I wish to participate' from multiple choice question, they will be taken to a further webpage where the option will be given to select a date on which to participate

1. Introduction and rationale

For intensive care staff in training, learning the steps in monitoring the function of an extracorporeal membrane oxygenator (ECMO) machine are fundamental concepts that form the basis on which their future practice will be built. The modality of this training is often practical in the form of an apprenticeship, shadowing experienced intensivists or perfusionists in order to learn their craft. We propose that if this initial training required more active participation in the form of a simulation, that trainees would learn these procedures more quickly and more reliably.

Over the past few years, emerging virtual reality (VR) applications have quickly gained broad attention within the medical field, including in cardiology and cardiothoracic surgery, as well as medical education more generally. Combining VR technology with head mounted displays (HMD), enables the design of a realistic, custom-built simulation in a 3 dimensional fully immersive environment [1]. Our group has developed a Virtual Reality (VR) simulation of the process of monitoring and performing a full circuit check for an ECMO patient. This Virtual Reality Extracorporeal Membrane Oxygenator Simulator (VR-ECMO sim) promises to update how we approach education of perfusionists and intensive care staff for their critical role.

In a related study on the VR-Extracorporeal Simulator (entitled “Virtual Reality Simulation as a Training Tool for Perfusionists in Extra Corporeal Circulation; Establishing Face and Content Validity” currently under peer-review), we showed that experts and novices alike found the simulator to be useful & realistic, and therefore valid for face and content validity. Due to the demonstration of feasibility in a closely related simulator, we aim to demonstrate face and content validity alongside concurrent validity in a single study for the VR-ECMO sim. We hypothesise that VR will enable participants to better learn and retain information through interactive engagement with a virtual reality ECMO simulator versus conventional training.

2. Objective(s)

In this study, the goal is to assess the face, content, and concurrent validity of the VR-ECMO sim by comparing the questionnaire ratings of novices and experts after completing the VR-ECMO sim, and comparing the novice intervention group who completed the VR-ECMO sim versus the control arm (video training) in terms of how well they are able to perform an ECMO circuit check, as rated by an expert.

3. Study type

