4.5 Sample size calculation

We calculated a required sample size of 32 novice participants (16 per group) in order to likely achieve statistically significant results in the Novice RCT arm. This is based on an alpha of 0.05, beta of 85, and a mean difference of 1. The expert group requires 10 participants in order to reasonably assess the face & content validity.

5. Methods

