7.1 Main study parameters/endpoints

The accuracy with which the predetermined sequence of steps involved in an ECMO circuit check is performed by the participant. This is defined as number of mistakes made, and amount of prompts/assistance required from the expert perfusionist present at the assessment. Additionally, time to

accurately perform the predetermined endpoints/steps in the protocol of performing a circuit check as defined in Appendix 3.

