7.4 Analysis

Please describe how the analysis will be done for the outcome parameters.

R version 4.2.2 will be used for analysis. Continuous data will be assessed for normal distribution using a Q-Q plot and Shapiro Wilk test. The data will be described as median (IQR) or means (SD) and compared using either an unpaired t-test or the Mann-Whitney U test (whichever is appropriate according to the distribution) will be used to determine significance. Categorical variables will be reported as numbers (%) and compared using a chi-squared test or fishers exact test (whichever is appropriate according to the distribution). All baseline characteristics and outcome data will be compared using abovementioned tests. In case of confounding variables, we will correct for these using Analysis of Covariance (ANCOVA). A P-value of <.05 will be considered statistically significant.

8. Ethical considerations

8 Regulation statement

The study will be conducted according to the principles of the Declaration of Helsinki (64th WMA General Assembly, Fortaleza, Brazil, October 2013), Gedragscode Gezondheidsonderzoek 2022 and in accordance with ISO 27799:2016(en) standards, regulations and Acts.

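### Mistakes, prompts and time all serve as main measures, with no single primary, success rule or multiplicity control; if any one significant result counted, the false-positive risk would lie above 5% and at most 14.3%

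*Combined protocol and SAP*

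**What the plan says.** The Summary, under primary outcomes, describes the accuracy of the sequence of steps, "defined as number of mistakes made and time taken, and amount of prompts/assistance required from the expert perfusionist". Time is part of that definition. The grammar leaves open whether prompts are inside it or alongside it.

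Section 7.1 starts from the same construct but says: "This is defined as number of mistakes made, and amount of prompts/assistance required from the expert perfusionist present at the assessment". Time follows in a separate sentence, as the time to "accurately perform the predetermined endpoints/steps in the protocol of performing a circuit check as defined in Appendix 3".

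The objective in section 2 compares the novice groups only "in terms of how well they are able to perform an ECMO circuit check, as rated by an expert", which names no measure.

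Section 4.5 gives the basis of the sample size: "This is based on an alpha of 0.05, beta of 85, and a mean difference of 1". It gives no outcome, unit or SD.

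Section 7.4 sets out the testing: "All baseline characteristics and outcome data will be compared using abovementioned tests", and "A P-value of <.05 will be considered statistically significant". It mentions no order of testing, combined score or adjustment. The Appendix 3 form has, for each of 13 steps, a yes/no for correct completion, a time to action and comments. It has no total score and no column for prompts.

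**The concern.** Two things are unsettled. The first is what is being measured. Total time taken and time to perform the steps accurately are different variables, and time is inside the definition of accuracy in one place and outside it in the other.

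The second is what result would make the trial positive. The measures can disagree: a participant may make fewer mistakes but take longer, or be saved from a mistake by a prompt. Without a rule, the same data could be reported as success or failure depending on which measure leads. If any one of the three may lead, the stated alpha of 0.05 no longer bounds the chance of a false claim.

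**Working it through.** **1. Does the sample size identify the primary?** With n per group = 2 × SD² × (z0.975 + z0.85)² / difference², reading the stated beta of 85 as 85% power and testing as two-sided, the SD implied by a difference of 1 is √(n/2) / (1.960 + 1.036).

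- 16 per group (section 4.5): 2.828 / 2.996 = 0.94.
- 22 per group (Summary): 3.317 / 2.996 = 1.11.

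No SD is stated, so neither size can be reproduced, and a difference of 1 could mean one mistake, one prompt or one minute. Section 4.5 does not show which measure is primary.

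**2. Error rate if any one of three counts.** Inputs: three tests at 0.05 each (section 7.4). Two-sided testing is assumed, since section 7.4 does not state it. The documents give no correlations, so a common value ρ is assumed and varied.

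- Independent measures: 1 − 0.95³ = 0.143. Favouring VR only: 1 − 0.975³ = 0.073.
- Correlated measures: 1 − ∫ [Φ((1.96 − √ρ·x)/√(1−ρ)) − Φ((−1.96 − √ρ·x)/√(1−ρ))]³ φ(x) dx. For VR only, the second Φ term is dropped.

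| Assumed ρ | At least one false difference | At least one favouring VR | All three significant |
|---|---|---|---|
| 0 | 14.3% | 7.3% | 0.01% |
| 0.3 | 13.6% | 6.8% | 0.1% |
| 0.5 | 12.5% | 6.3% | 0.3% |
| 0.7 | 10.9% | 5.5% | 0.9% |
| 0.9 | 8.4% | 4.2% | 2.3% |
| 0.95 | 7.3% | 3.7% | 3.0% |
| 0.99 | 6.0% | 3.0% | 4.0% |

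The reference values are 5% for the second column and 2.5% for the third. Both columns fall to those values as ρ nears 1, so the range has no natural floor above them. Simulated t-tests at 16 and 22 per group agree: about 14% at ρ = 0 and 8.2% to 8.5% at ρ = 0.9.

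The 7.3% maximum for VR assumes correlations that are not negative. If speed traded off against accuracy, the limit would be 3 × 0.025 = 7.5%.

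**3. Where the correlation might lie.** Full independence is unlikely. All three measures come from one assessment, and the expert is there "to provide prompts when a student is unsure how to perform a certain step", which ties prompts to uncertainty about the steps. If mistakes and prompts correlate at 0.7 and time is unrelated to both, the figures are 12.9% and, favouring VR, 6.6%.

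**4. Two primary measures.** If section 7.1 is read as making time subordinate, the two-sided figure is 1 − 0.95² = 9.8% when independent, 9.1% at ρ = 0.5 and 7.0% at ρ = 0.9.

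**5. All three required.** The last column of the table stays below 5% throughout, so there is no inflation under that rule.

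**The case against.** The strongest reply is that the plan has one primary construct, accuracy of the circuit check, and that both sections list the same three components. That is right as far as it goes. A reader might infer that the Summary and section 7.1 name different endpoints, and they do not. The differences are whether time belongs to accuracy and what time means. But a single construct with several components needs a score or a rule, and none is given.

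A second reply is that the inflation is hypothetical. It depends on an any-one rule that the plan never states, on unknown correlations and on assumed two-sided tests. This also stands. A reader might infer that the trial runs a 14% false-positive rate, but the documents support that figure only as a ceiling, under one reading and with independent measures. Because the hypothesis favours VR, the smaller figures for a false result in that direction are arguably the more relevant ones.

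Third, the Summary says that those who collect and analyse the data are blinded, and section 12 requires changes to the analysis to be submitted for approval. Both limit selective choice, and nothing in the documents suggests that such a choice is intended. Neither supplies a success rule, and neither alters the error rate of several unadjusted tests.

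**Conclusion.** The concern holds in conditional form. What the text shows directly is that accuracy and time are defined in two ways, and that no single primary, combining score, success rule or multiplicity control is given.

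The size depends on the rule eventually applied. If any one result suffices, the two-sided error is above 5% and at most 14.3%, and the chance of a false result favouring VR is above 2.5% and at most 7.3%. With two primary measures the two-sided maximum is 9.8%. With all three required there is no excess. These figures rest on two-sided tests and assumed correlations.

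Confidence is high in the ambiguity and lower in any particular error rate. The point should be settled before analysis because it decides how the main result is read.

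**What to change.** Before any analysis:

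- Use one definition of accuracy and one definition of time in the Summary, section 2 and section 7.1.
- Name a single primary endpoint, chosen by the investigators. If it is the number of Appendix 3 steps not completed correctly, state how a step completed only after a prompt is scored, since the form has no place for prompts.
- Make the other two measures secondary, reported with estimates and 95% confidence intervals and not used to declare success.
- In section 4.5, state which outcome and SD the difference of 1 refers to. If it is not the chosen endpoint, restate the power for that endpoint at the planned size. It is not enough to assert that the existing calculation applies, because it names no outcome and its total of 32 conflicts with the Summary's 44.
- If all three stay primary, state the success rule. If any one can succeed, test them with Holm at overall 0.05.

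The cost is a protocol amendment submitted for approval under section 12. Naming one primary needs no split of alpha.

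Holm lowers power per outcome at its first step (0.05/3 = 0.0167). By noncentral t with difference 1 and an assumed SD of 1, power falls from 78% to 62% at 16 per group and from 90% to 79% at 22 per group. If all three measures truly differ by 1 SD with correlation 0.5, later Holm steps recover part of the loss, giving about 70% and 86% per outcome. These are illustrations, since the documents give no SD.

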4.2. Population (base)

As above; Our study will recruit from two populations for the expert and novice arms of this study. For the former, 10 experts who are experienced perfusionists/intensivists with more than 6 years of experience with ECMO will be included. For the novice arm, the population will include intensive care nurses & cardiothoracic surgery nurses who work at one of the academic hospitals in the Netherlands, with no prior experience with ECMO.

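### The novice allocation states no ratio, blocking or stratification, so neither equal groups nor a balanced mix of nurse units is ensured, and a cheap remedy exists

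*Combined protocol and SAP*

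**What the plan says.** The Summary (Methods, Novice Arm) states: "Novice participants will be allocated a study ID from 1-50 at the point of recruitment and randomised by an online research randomiser". Under Randomisation it adds that the tool is used "to generate a group allocation for the participant according to their study ID number". Neither place, nor any other, gives an allocation ratio, a block size, a stratification factor, or who holds the allocations.

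Two target sizes are given, both with equal groups. The Summary (Recruitment and consent) says: "We calculated a required sample size of 44 novice participants (22 per group) in order to likely achieve statistically significant results". Section 4.5 says: "We calculated a required sample size of 32 novice participants (16 per group", and continues: "This is based on an alpha of 0.05, beta of 85, and a mean difference of 1". No standard deviation or dropout allowance is stated, so nothing links 50 IDs to 44 or 32.

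Section 4.2 draws novices from "intensive care nurses & cardiothoracic surgery nurses who work at one of the academic hospitals in the Netherlands". Section 4.3 is wider and admits any nurse at such a hospital. The Methods paragraph of the Summary is narrower and describes novices as intensive care staff. Section 4.4 excludes people with earlier ECMO experience.

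Appendix 1 records job title, years of work, and gaming, VR and simulation experience. Section 7.4 compares all baseline characteristics between groups by significance test and plans ANCOVA if confounding is found. It names no covariate.

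**The concern.** The sample size assumes equal groups, but the stated procedure does not secure them if recruitment stops at 44 or 32.

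The second part matters more. Appendix 3 scores 13 steps. Some are specific to the ECMO circuit, but others, such as alarm limits, gas settings, the heparin pump and laboratory results, resemble general bedside monitoring. Unit of work could therefore plausibly affect mistakes, prompts and time, whatever the training. With 16 to 22 per arm, an uneven split of units could blur or exaggerate the comparison in this one trial.

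The planned adjustment does not settle this. It depends on what is seen in the data, and baseline tests have little power at this size. The choice of covariates also stays open until after the results are known.

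**Working it through.** **Inputs.** From the documents: 50 IDs; targets of 44 (22 per group) and 32 (16 per group); alpha 0.05; a power figure of 85 (printed as beta); mean difference 1. Assumed: SD 1 and a two-sided test for the power figures; intensive care share of 50 to 90%, since the mix is not given.

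**1. The plan's own sample size.** Without an SD, 16 per group cannot be reproduced. With SD = 1, two-sided 0.05 and 85% power, n per group = 2 × (1.960 + 1.036)² / 1² = 17.96, so 18 (19 with the t distribution). By the same normal formula, 16 per group implies SD = √(16/17.96) ≈ 0.94, and 22 implies SD = √(22/17.96) ≈ 1.11.

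**2. Chance of exactly equal groups.** Two readings of the procedure are possible.
- Balanced 25/25 list of which the first n IDs are used, P = C(25, n/2)² / C(50, n): 0.333 at n = 44; 0.231 at n = 32.
- Independent draws, P = C(n, n/2) / 2ⁿ: 0.120 at n = 44; 0.140 at n = 32.

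Under the balanced list the groups differ by at most 2 with probability 81% at 44, and the largest possible difference there is 6 (19/25). If all 50 IDs are used, a balanced list gives exactly 25/25.

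**3. Power cost of unequal sizes** (difference 1, SD 1, two-sided t-test).
- n = 44: 90.0% at 22/22; 89.4% at 19/25; 87.6% at 16/28.
- n = 32: 78.1% at 16/16; 76.7% at 13/19; 71.8% at 10/22.

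The loss is small except in an extreme split.

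**4. Unit mix with equal arms and no stratification.** Let K of n novices be intensive care nurses and m = n/2. The number X in one arm is hypergeometric (n, K, m), and the gap in share is |2X − K| / m. For example, at n = 32 and K = 16 a gap of 20 points or more needs X ≤ 6 or X ≥ 10, with probability 0.289.

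| Assumed share | n = 32: K | P(gap ≥ 20 points) | n = 44: K | P(gap ≥ 20 points) |
|---|---|---|---|---|
| 50% | 16 | 28.9% | 22 | 13.1% |
| 60% | 19 | 14.9% | 26 | 12.4% |
| 70% | 22 | 25.2% | 31 | 18.5% |
| 80% | 26 | 17.2% | 35 | 13.2% |
| 90% | 29 | 0% | 40 | 0% |

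The figures jump because only a few gaps are possible at each K. Over every whole K between these 50% and 80% rows the range is 8-29% at n = 32 and 7-23% at n = 44. If arm sizes are also left to chance, simulation gives about 18-28% at 32 and 10-20% at 44 for shares of 50-80%. At a 90% share it gives about 6% at 32 and at most 2% at 44.

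**5. What a gap would do.** If units differed by δ, a gap g shifts the arm comparison by g × δ. With δ = 1 SD (assumed) and g = 0.20, the shift is 0.20 SD. Ignoring unit in a half-and-half sample adds 0.5 × 0.5 × δ² to the outcome variance: 25% for δ = 1 SD, 6% for δ = 0.5 SD.

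**6. Effect of stratified blocks.** With blocks of 4 within unit type and a 60% share, simulated group sizes are equal in about 63% of runs and within 2 in about 99%. The unit gap is at most 9 points at n = 44 and 12.5 at n = 32. With blocks of 4 and 6 in random order and shares of 50-80% (20,000 runs each), sizes are equal in 47-65% of runs and within 2 in about 97-98%. The largest gap is 14 points at n = 44 and 19 at n = 32, so 20 points is never reached.

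**The case against.** Unrestricted randomisation is valid. Chance imbalance is not bias, and the test's error rate already allows for it. This stands, so the cost is precision and the credibility of a single small result.

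A reader might infer that a material imbalance in prior skill is likely. The documents do not support that. A 20-point gap in unit mix has well under even odds; only a gap of about 10 points comes near even odds (roughly 46-60% for shares of 50-80% when arm sizes are left to chance). The calculation also covers unit mix, not skill. No section reports a performance difference between units, earlier ECMO experience is excluded, and many Appendix 3 steps concern the circuit itself. If the sample is mostly intensive care nurses, as one line of the Summary suggests, the issue nearly vanishes.

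A reader might also infer that one unblocked list is used. The documents name only the tool and the ID range. The exact statement is that the method is not specified, so equality is not ensured. Stopping short of 50 is likewise an inference: 50 may be an unstated allowance for loss (44 / 0.88 = 50).

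Finally, section 7.4 does offer a response to imbalance. It is a real provision, but it is conditional and names no covariate, so it does not replace a prespecified factor.

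**Conclusion.** The point holds as a minor, inexpensive improvement. The plan does not specify an allocation method that ensures the equal groups it states, though the power lost through unequal sizes is small. Nor does it balance or prespecify unit type. With equal arms, the chance of a unit-mix gap of 20 points or more is about 15-29% at 32 and 12-19% at 44 for assumed intensive care shares of 50, 60, 70 and 80%, and near zero at 90%. Whether such a gap matters rests on an unquantified link between unit type and performance, which is plausible but not shown. The validity of the randomised comparison is not in question.

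**What to change.** - Reconcile 32, 44 and 50, and say whether 50 includes an allowance for loss.
- Ask for unit at sign-up; the page currently takes only name and contact details.
- Randomise 1:1 in permuted blocks of varying size within unit type, for example 4 and 6. Avoid blocks of 2, because participants and training staff are unblinded and the second allocation in each block could be guessed.
- Define the strata as intensive care versus other, since section 4.3 admits any nurse.
- Keep the list concealed from those who enrol, and state who holds it.
- In section 7.4, include unit type as a prespecified factor in the analysis of the main measures, whatever imbalance is observed, in place of a decision made after baseline testing.

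The cost is one sign-up question, two short lists and one degree of freedom. Incomplete blocks will leave small differences in group size and unit mix, as shown in step 6. The documents do not show whether the named online tool can produce such lists; if it cannot, they can be generated in R, which section 7.4 already names. If stratification is not wanted in so small a trial, stating the ratio and method and prespecifying unit type as a factor would still recover most of the benefit.
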